**Table 2. Study Objectives, Endpoints, and Estimands**

Primary Immunogenicity Objectives	Estimands	Primary Immunogenicity Endpoints

 
• To evaluate the immunogenicity of TBE vaccine 0.5 mL by NT.
 
• To evaluate the immunogenicity of TBE vaccine 0.25 mL by NT.
 
	
 
• In healthy Japanese adult participants 16 years of age and older who received 3-dose TBE vaccine 0.5 mL in compliance with the key protocol criteria (evaluable participants): The proportion who are seropositive (achieving NT titer <math>\geq 1:10</math>) 4 weeks after the third dose.
 
• In healthy Japanese pediatric participants <math>\geq 1</math> to <math><16</math> years of age who received 3-dose TBE vaccine 0.25 mL in compliance with the key protocol criteria (evaluable participants): The proportion who are seropositive (achieving NT titer <math>\geq 1:10</math>) 4 weeks after the third dose.
 
	TBEV-neutralizing antibody titers.

**Table 2. Study Objectives, Endpoints, and Estimands**

Primary Safety Objectives	Estimands	Primary Safety Endpoints

 
• To evaluate the safety profile of TBE vaccine 0.5 mL.
 
• To evaluate the safety profile of TBE vaccine 0.25 mL.
 
	
In healthy Japanese participants from each age group receiving at least 1 dose of investigational product:
 
 
• The percentage of participants reporting local reactions within 7 days after each vaccination.
 
• The percentage of participants reporting systemic events within 7 days after each vaccination.
 
• The percentage of participants reporting AEs within 1 month after each dose.
 
• The percentage of participants reporting SAEs during the study period.
 
	
 
• Prespecified local reactions (redness, swelling, and pain at the injection site).
 
• Prespecified systemic events (fever, decreased appetite, drowsiness, and irritability for participants 1 to <math>\leq</math>2 years of age; and fever, fatigue, headache, vomiting, diarrhea, muscle pain, and joint pain for participants <math>></math>2 years of age).
 
• AEs within 1 month after vaccination.
 
• SAEs throughout the study.
 

Secondary Immunogenicity Objectives	Estimands	Secondary Immunogenicity Endpoints

 
• To describe the immunogenicity of TBE vaccine 0.5 mL by NT.
 
• To describe the immunogenicity of TBE vaccine 0.25 mL by NT.
 
	
In healthy Japanese adult participants 16 years of age and older who received 3-dose TBE vaccine 0.5 mL in compliance with the key protocol criteria (evaluable participants):
 
 
• The proportion who are seropositive (achieving NT titer <math>\geq</math>1:10) 4 weeks after the second dose.
 
• NT GMTs 4 weeks after the second and 4 weeks after the third dose.
 
• NT GMFRs 4 weeks after the second and 4 weeks after the third dose as compared to baseline.
 
• NT GMFR 4 weeks after the third dose as compared to 4 weeks after the second dose.
 
 
In healthy Japanese pediatric participants 1 through 15 years of age who received 3-dose TBE vaccine 0.25 mL in compliance with the key protocol criteria (evaluable participants):
 
 
• The proportion who are seropositive (achieving NT titer <math>\geq</math>1:10) 4 weeks after the second dose.
 
	TBEV-neutralizing antibody titers.

**Table 2. Study Objectives, Endpoints, and Estimands**

Forest plot showing NT GMTs and NT GMFRs for various treatments across three time points: baseline, 4 weeks after the second dose, and 4 weeks after the third dose. The y-axis lists treatments: CCI, Sputum, Saliva, Urine, and Blood. The x-axis shows the difference in log scale. Red squares indicate significant differences.

- NT GMTs 4 weeks after the second and 4 weeks after the third dose.
- NT GMFRs 4 weeks after the second and 4 weeks after the third dose as compared to baseline.
- NT GMFR 4 weeks after the third dose as compared to 4 weeks after the second dose.

Treatment	Baseline	4 weeks after 2nd dose	4 weeks after 3rd dose
CCI	0.00	0.00	0.00
Sputum	0.00	0.00	0.00
Saliva	0.00	0.00	0.00
Urine	0.00	0.00	0.00
Blood	0.00	0.00	0.00

**Table 2. Study Objectives, Endpoints, and Estimands**

		
--	--	--

## 2.2. Study Design

This Phase 3, multicenter, single-arm, open-label study will be conducted at investigator sites in Japan. This study is part of the Phase 3 clinical development plan to support use of TBE vaccine 0.5 mL and 0.25 mL in healthy Japanese adults ( $\geq 16$  years of age) and the pediatric population ( $\geq 1$  to  $< 16$  years of age). The purpose of this study is to provide key safety and immunogenicity data in Japanese participants. Study duration is approximately 7 to 15 months for each participant. Approximately 100 adults ( $\geq 16$  years of age at the time of consent) and 65 children ( $\geq 1$  to  $< 16$  years of age at the time of consent) will be enrolled to receive investigational product such that approximately 150 evaluable participants complete the study.

Vaccinations will occur at Visits 1, 2, and 4 and blood draw will be taken prior to the first dose (Visit 1), 1 month after the second dose (Visit 3), prior to the third dose (Visit 4), and 1 month after the third dose (Visit 5) to assess immune responses (Section 1.3 of the protocol).

Local reactions (redness, swelling, and pain at the injection site), systemic events (fever, decreased appetite, drowsiness, and irritability for participants 1 to  $\leq 2$  years of age; and fever, fatigue, headache, vomiting, diarrhea, muscle pain, and joint pain for participants  $> 2$  years of age), and use of antipyretic/pain medication will be collected in the e-diary within 7 days after each vaccination.

AEs will be collected from the time the participant/parent(s)/legal guardian/legally authorized representative provides informed consent, through and including Visit 3, and from Visit 4 to Visit 5. SAEs will be collected throughout the study.

No data monitoring committee will be established for the study.

## 3. ENDPOINTS AND BASELINE VARIABLES: DEFINITIONS AND CONVENTIONS

### 3.1. Primary Endpoint

- TBEV-neutralizing antibody levels
  - These will be determined 4 weeks after the third dose using Adner NT assay for the analysis of the primary estimands.

- To support the primary estimands, an NT titer will be classified as seropositive if the titer is  $\geq 1:10$  at each time point.

### 3.2. Secondary Endpoints

- TBEV-neutralizing antibody levels
  - These will be determined at baseline, 4 weeks after the second dose, and before the third dose using Adner NT assay for the analysis of the secondary estimands.
  - To support the secondary estimands, an NT titer will be classified as seropositive if the titer is  $\geq 1:10$  at each time point.
  - To support the secondary estimands, the NT fold rise between the following time points will be calculated:
    - Baseline and 4 weeks after the second dose
    - Baseline and 4 weeks after the third dose
    - 4 Weeks after the second dose and 4 weeks after the third dose

CCI

Race and Ethnicity Group	Percentage
White	85
Asian	75
Pacific Islander	75
Black	65
American Indian	55
Alaskan Native	55
Black	50

### 3.4. Baseline and Other Variables

### 3.4.1. Demographics, Medical History, and Physical Examination

The demographic variables are age (in years) at the time of informed consent (Day 1), sex, race, and ethnicity.

Age at Day 1 will be directly calculated based on the participant's date of birth recorded in the CRF. For example, if the vaccination day is 1 day before the participant's 21st birthday, the participant is considered to be 20 years of age.

Day 1 is also defined as the day of the first vaccination and the start of the subsequent reporting period for local reactions and systemic events in the e-diary.

Day 1 is considered the baseline visit for the immunogenicity assessments.

Medical history will be categorized according to MedDRA.

Physical examination (at Visit 1) will include, at a minimum, assessments of the cardiovascular, respiratory, gastrointestinal, and neurological systems. Height and weight will also be measured and recorded. Prior to subsequent vaccination (at Visits 2 and 4), physical examination should be performed if the clinical assessment indicates that it is necessary to comprehensively evaluate the participant.

CC1

### 3.4.2. E-Diary Transmission

An e-diary will be considered transmitted if any data for the local reactions, systemic events, or use of antipyretic/pain medication are present for any day. If all data are missing for all items on the e-diary for all 7 days after vaccination, then the e-diary will be considered not transmitted. An e-diary will be considered completed if all expected data for all 7 days are available (ie, not missing). Otherwise, the e-diary will be considered incomplete. For any given day, an e-diary will be considered complete if all expected data are available.

### 3.4.3. Prior/Concomitant Nonstudy Vaccines and Concomitant Treatments

The name and date of administration for any nonstudy vaccinations received from the time of signing of the ICD until the final visit will be collected and recorded in the CRF.

History of JEV vaccination of participants will be collected at Visit 1 as completely as possible.

Nonstudy vaccines and medications taken during the study will be categorized according to the WHO Drug Dictionary and summarized in accordance with the sponsor reporting standards.

### 3.5. Safety Endpoints

### 3.5.1. Adverse Events

AEs will be captured and reported in accordance with Pfizer reporting standards.

The time period for actively eliciting and collecting AEs and SAEs (“active collection period”) for each participant begins from the time the participant/parent(s)/legal guardian/legally authorized representative provides informed consent, which is obtained before the participant’s participation in the study (ie, before undergoing any study-related procedure and/or receiving investigational product), through and including Visit 3, and from Visit 4 to Visit 5. Between Visit 3 and Visit 4, only SAEs will be reported.

For participants who are screen failures, the active collection period ends when screen failure status is determined.

If the participant withdraws from the study and also withdraws consent for the collection of future information, the active collection period ends when consent is withdrawn.

If a participant definitively discontinues or temporarily discontinues investigational product because of an AE or SAE, the AE or SAE must be recorded on the CRF and the SAE reported using the Vaccine SAE Reporting Form.

Both nonserious AEs and SAEs are recorded on the CRF and will be categorized according to the current version (at the time of reporting) of MedDRA.

An immediate AE is defined as any AE that occurred within the first 30 minutes after administration of the investigational product.

The following AEs will be summarized at the participant level:

- AEs reported within 1 month after the first dose (from Visit 1 to Visit 2).
- AEs reported within 1 month after the second dose (from Visit 2 to Visit 3).
- AEs reported within 1 month after the third dose (from Visit 4 to Visit 5).
- AEs reported during the vaccination phase.
- Related AEs, severe AEs, related severe AEs, life-threatening AEs, related life-threatening AEs, AEs leading to discontinuation, related AEs leading to discontinuation, and immediate AEs will be summarized in the same way.
- SAEs reported from the first dose until 1 month after the third dose.
- Related SAEs will be summarized in the same way.

### 3.5.2. Reactogenicity Data

Reactogenicity data are prompted AEs collected using an e-diary, during Days 1 through 7, starting on the day of each vaccination. The reactogenicity data will include local reactions (pain, redness, and swelling at the injection site) and systemic events (decreased appetite, drowsiness, and irritability for participants 1 to  $\leq$ 2 years of age; and fever, fatigue, headache, vomiting, diarrhea, muscle pain, and joint pain for participants  $>$ 2 years of age).

### 3.5.2.1. Local Reactions

Local reactions reported in the e-diary are redness, swelling, and pain at the injection site.

### Presence of Local Reactions (Proportion of Participants Reporting)

The participant or participant's legally acceptable representative/parent/legal guardian will record the presence or absence of pain at the injection site in the e-diary as "mild," "moderate," "severe," or "none". Redness and swelling will be measured and recorded in measuring device units and then categorized during analysis as mild, moderate, or severe based on the grading scale in [Table 3](#), [Table 4](#), and [Table 5](#). Measuring device units can be converted to centimeters according to the following scale: 1 measuring device unit = 0.5 cm. The participant or participant's parent(s)/legal guardian(s) will be prompted to contact the investigator if the participant experiences a severe (Grade 3 or above) local reaction to assess the reaction and to perform an unscheduled assessment or visit as appropriate.

Only an investigator is able to classify a participant's local reaction as Grade 4, after physical examination of the participant or documentation from another medically qualified source (eg, emergency room or hospital record) or, in the case of pain at the injection site only, contact with the participant. If a participant experiences a Grade 4 local reaction, the investigator must immediately notify the sponsor. Grade 4 reactions will be collected on the unscheduled reactogenicity page and as an AE on the CRF.

The AE event will be graded using the AE intensity grading scale as indicated in the table “Assessment of Intensity” in Section 10.3 of the protocol.

The presence or absence of each local reaction on a given day is defined as follows:

- = “Missing,” if the value is missing on a given day;
- = “Yes,” if the participant reports the reaction as “yes” for redness or swelling (with a specific diameter or more as defined in Table 3, Table 4, and [Table 5](#)) or “mild,” “moderate,” “severe,” or “Grade 4” for pain at the injection site on a given day;
- = “No,” if the participant reports the reaction as “no” for redness or swelling or “none” for pain at the injection site on a given day.

### **Grading Scale for Local Reactions**

The grading of local reactions is listed below in Table 3, Table 4, and [Table 5](#).

#### **Participants 1 to $\leq$ 2 Years of Age**

**Table 3. Grading Scale for Local Reactions for Participants 1 to  $\leq$ 2 Years of Age**

	Mild Grade 1	Moderate Grade 2	Severe Grade 3a	Grade 4b
Redness	>0 cm to 2.0 cm (1 to 4 measuring device units)	>2.0 cm to 7.0 cm (5 to 14 measuring device units)	>7.0 cm (>14 measuring device units)	Necrosis or exfoliative dermatitis b
Swelling	>0 cm to 2.0 cm (1 to 4 measuring device units)	>2.0 cm to 7.0 cm (5 to 14 measuring device units)	>7.0 cm (>14 measuring device units)	Necrosis b
Pain at the injection site (tenderness)	Hurts if gently touched (eg, whimpers, winces, protests, or withdraws)	Hurts if gently touched with crying	Causes limitation of limb movement	Emergency room visit or hospitalization for severe pain at the injection site

- a. Participants experiencing local reactions >14 caliper units (>7.0 cm) are to be seen by or contact the study site; an unscheduled visit may be required.
- b. Grade 4 assessment must be made by an investigator; Grade 4 will not be collected in the e-diary but will be collected in the case report form. The severity of the local reaction should be graded using the AE severity grading scale provided in the protocol.

#### **Participants >2 to $<$ 12 Years of Age**

**Table 4. Grading Scale for Local Reactions for Participants >2 to  $<$ 12 Years of Age**

	Mild Grade 1	Moderate Grade 2	Severe Grade 3a	Grade 4b
Redness	>0 cm to 2.0 cm (1 to 4 measuring device units)	>2.0 cm to 7.0 cm (5 to 14 measuring device units)	>7.0 cm (>14 measuring device units)	Necrosis or exfoliative dermatitis b

**Table 4. Grading Scale for Local Reactions for Participants >2 to <12 Years of Age**

	Mild Grade 1	Moderate Grade 2	Severe Grade 3a	Grade 4b
Swelling	>0 cm to 2.0 cm (1 to 4 measuring device units)	>2.0 cm to 7.0 cm (5 to 14 measuring device units)	>7.0 cm (>14 measuring device units)	Necrosis b
Pain at the injection site	Does not interfere with activity	Interferes with activity	Prevents daily activity	Emergency room visit or hospitalization for severe pain at the injection site

- a. Participants experiencing local reactions >14 caliper units (>7.0 cm) are to be seen by or contact the study site; an unscheduled visit may be required.
- b. Grade 4 assessment must be made by an investigator; Grade 4 will not be collected in the e-diary but will be collected in the case report form. The severity of the local reaction should be graded using the AE severity grading scale provided in the protocol.

**Participants ≥12 Years of Age****Table 5. Grading Scale for Local Reactions for Participants ≥12 Years of Age**

	Mild Grade 1	Moderate Grade 2	Severe Grade 3a	Grade 4b
Redness	>2.0 cm to 5.0 cm (5 to 10 measuring device units)	>5.0 cm to 10.0 cm (11 to 20 measuring device units)	>10 cm (>20 measuring device units)	Necrosis or exfoliative dermatitis b
Swelling	>2.0 cm to 5.0 cm (5 to 10 measuring device units)	>5.0 cm to 10.0 cm (11 to 20 measuring device units)	>10 cm (>20 measuring device units)	Necrosis b
Pain at the injection site	Does not interfere with activity	Interferes with activity	Prevents daily activity	Emergency room visit or hospitalization for severe pain at the injection site

- a. Participants experiencing local reactions >20 caliper units (>10 cm) are to be seen by or contact the study site; an unscheduled visit may be required.
- b. Grade 4 assessment must be made by an investigator; Grade 4 will not be collected in the e-diary but will be collected in the case report form. The severity of the local reaction should be graded using the AE severity grading scale provided in the protocol.

For each local reaction, the derivation of whether or not the specific reaction occurred on “any day (Day 1-7)” will be made. The derivation of this variable is given in Table 6 below.

**Table 6. Derived Variables for Each Local Reaction**

Variablea	Yes (1)	No (0)	Missing (.)
Any day (Day 1-7)	Participant reports the reaction as “yes” on any day from Day 1 through Day 7.	Participant reports the reaction as “no” on all 7 days or as a combination of “no” and missing on all 7 days.	Participant’s response to the reaction is missing on all 7 days.

- a. The variable will be defined for each of the 3 local reactions.

For “any local reaction” on any day, a similar definition can be applied as given in Table 7 below.

**Table 7. Derived Variables for Any Local Reaction**

Variable	Yes (1)	No (0)	Missing (.)
Any day (Day 1-7)	Participant reports any reaction as “yes” on any day during Days 1 through 7.	Participant reports all reactions as “no” on all 7 days or as a combination of “no” and missing on all 7 days for all 3 local reactions.	Participant’s response to all of the local reactions is missing on all 7 days.

### Maximum Severity for Local Reactions

The maximum severity (highest grading) of each local reaction within 7 days after each vaccination will be derived. The maximum severity will be derived as follows:

- = “Missing,” if values are missing for all days from Day 1 through Day 7 after each vaccination;
- = 0, if the participant reports all reactions as “no” or a combination of missing and “no” for all days from Day 1 through Day 7 after each vaccination;
- = *highest grade* (maximum severity) within 7 days after each vaccination if the answer is not “no” for at least 1 day.

### Duration of Each Local Reaction

The duration of each local reaction will be calculated in days as (resolution date of reaction - start date of reaction + 1). Resolution of the reaction is the last day on which the reaction is recorded in the e-diary or the date the reaction ends if it is unresolved during the participant diary-recording period (end date collected on the CRF), unless chronicity is established. If there is no known end date, the duration will be considered unknown and set to missing. However, if a reaction is ongoing at the time of a subsequent vaccination, the end date/day for the ongoing event would be the date/day that the next vaccine is administered, which will be used for the duration computation.

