6.1. Study Intervention(s) Administered

Intervention Name	Tick-borne encephalitis vaccine, PF-06830414		
Type	Biologic		
Dose Formulation	Suspension for injection in a pre-filled syringe		
Composition of TBE Vaccines			
	Composition of a Single Dose	FSME-IMMUN 0.25 mL	FSME-IMMUN 0.5 mL
	Formaldehyde-inactivated TBEV ^a	Target 1.2 µg (range 1.00-1.38 µg)	Target 2.4 µg (range 2.00-2.75 µg)
	Aluminum hydroxide, hydrated	0.17 mg Al ³⁺	0.35 mg Al ³⁺
	Human serum albumin	0.25 mg	0.5 mg
	Sodium chloride	1.725 mg	3.45 mg
	Disodium hydrogen phosphate	0.11 mg	0.22 mg
	Potassium dihydrogen phosphate	0.023 mg	0.045 mg
	Water for injection	ad 0.25 mL	ad 0.5 mL
	a. Produced using a CC working virus seed and consisting of a sterile suspension of formaldehyde-inactivated and sucrose gradient purified TBEV antigen.		
Unit Dose Strength(s)	
2.4 µg/0.5 mL (for participants ≥16 years of age)1.2 µg/0.25 mL (for participants ≥1 to <16 years of age)		
Dosage Level(s)	1st dose 0.5 mL or 0.25 mL 2nd dose (21-35 days after 1st dose) 0.5 mL or 0.25 mL 3rd dose (150-365 days after 2nd dose) 0.5 mL or 0.25 mL		
Route of Administration	Intramuscular		
IMP or NIMP	IMP		
Sourcing	Provided centrally by the sponsor		
Packaging and Labeling	Study intervention will be provided in an open-label carton that includes 1 prefilled syringe. Each carton will be labeled as required per country requirement.		

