8.11.2. Visit 2 (Dose 2 Visit, 21-35 Days After Visit 1 [Dose 1])

- Ensure and document that the participant continues to be eligible for the study (see [Section 7.2](#) for participant discontinuation/withdrawal) and none of the temporary delay criteria are met ([Section 5.5](#)).
- Record nonstudy vaccinations administered since Visit 1, as described in [Section 6.5](#).
- Record concomitant medications used to treat SAEs since Visit 1, as described in [Section 6.5](#).
- Review the participant's e-diary data with the participant or participant's parent(s)/legal guardian(s); collect stop dates of any e-diary events ongoing on the last day that the e-diary was completed and record stop dates in the CRF.
- Determine whether any AEs (includes nonserious AEs and SAEs) have occurred since the previous visit and follow up on any previously reported events to determine the outcome (ie, record stop dates or confirm if they are still continuing) and record as described in [Section 10.3](#), and record concomitant medications used to treat SAEs.

- Measure and record the participant's axillary temperature (°C).
- For female participants of childbearing potential: Discuss contraceptive use and perform a urine pregnancy test. The result of pregnancy test must be confirmed before administration.
- Investigator or delegated site staff will administer a single 0.5-mL or 0.25-mL injection of TBE vaccine into the deltoid muscle (or anterolateral thigh, if the participant is <18 months of age).

After vaccination:

- Investigator or delegated site staff will observe the participant for 30 minutes after vaccination for any reactions.
- Record any AEs on the CRF and on an SAE form as applicable. Record concomitant medications used to treat SAEs.
- Confirm that the e-diary is working and review instructions if necessary. Remind the participant or participant's parent(s)/legal guardian(s) to complete the e-diary for 7 days after the day of vaccination. Provide a thermometer or measuring device if needed.

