### 3.5.2.2. Systemic Events

Systemic events reported via the e-diary are fever, decreased appetite, drowsiness, and irritability for participants 1 to  $\leq$ 2 years of age; and fever, fatigue, headache, vomiting, diarrhea, muscle pain, and joint pain for participants  $>$ 2 years of age. The participant or participant’s legally acceptable representative/parent/legal guardian is to document the presence or absence of systemic events in the e-diary as “mild,” “moderate,” “severe,” or “none”. The participant or participant’s legally acceptable representative/parent/legal guardian is to be asked to assess the severity of each event according to Table 8 and [Table 9](#) below.

Only an investigator is able to classify a participant’s systemic event as Grade 4, after physical examination of the participant or documentation from another medically qualified source (eg, emergency room or hospital record) or contact with the participant. If a participant experiences a Grade 4 systemic event, the investigator must immediately notify the sponsor. A Grade 4 event will be collected on the unscheduled reactogenicity page and as an AE on the CRF. The event will be graded using the AE severity grading scale (see Section 10.3 of the protocol). Further, for all ongoing systemic events on Day 7, the stop date will be recorded in the CRF.

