### **6.1.2.2. Reactogenicity Data**

#### **6.1.2.2.1. Local Reactions**

- Endpoints: Participants reporting local reactions (redness, swelling, and pain at the injection site) and severity of the reactions ([Section 3.5.2.1](#)).
- Analysis time points: 7-Day period following each vaccination.
- Analysis population: Safety population ([Section 4](#)).
- Reporting summaries:
  - Maximum severity for local reactions  
The number of participants reporting e-diary data transmitted for at least 1 day (these values are used as the denominators for the percentage calculations), the number of participants reporting at least 1 occurrence of the specified reaction or any reaction by the maximum severity grade, the observed proportion of participants, and their exact 2-sided CIs (Clopper and Pearson).
  - Duration of each local reaction  
Number of participants reporting the specified reaction, mean, median, range (minimum, maximum), standard deviation, and number of unknown durations.
  - Onset of local reactions  
The number of participants reporting the specified reaction or any reaction, mean, range (minimum, maximum), and standard deviation.
  - Figures  
A bar graph showing the percent incidence for the specified reaction and for any reaction, by day.

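### Reactions still present at the next vaccination are tabulated as completed durations without being flagged, so for persistent reactions the mean, SD and maximum are not comparable across doses

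*SAP*

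**What the plan says.** SAP 3.5.2.1 (Duration of Each Local Reaction) counts duration from start date to resolution date, both days included. Four rules fix the end date:

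- If the reaction resolves within the diary period, the end is the last day on which it was recorded.
- If it outlasts the diary, the end is "the date the reaction ends if it is unresolved during the participant diary-recording period (end date collected on the CRF), unless chronicity is established". The SAP does not say what value applies once chronicity is established.
- "If there is no known end date, the duration will be considered unknown and set to missing".
- As an exception, "if a reaction is ongoing at the time of a subsequent vaccination, the end date/day for the ongoing event would be the date/day" on which the next vaccine is given, and that date is used in the calculation.

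SAP 3.5.2.2 says that the systemic event variables are derived in a similar way. SAP 6.1.2.2.1 then reports, for each local reaction, the number of participants reporting it with "mean, median, range (minimum, maximum), standard deviation, and number of unknown durations". SAP 6.1.2.2.2 uses the same layout for systemic events. Neither section has an entry for durations that were cut at the next dose.

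**The concern.** The exception applies only when the reaction is known to be continuing, so the date it assigns cannot be the resolution date. The resulting number is a lower bound. Because it is not missing, it is not counted among the unknown durations, and it enters the mean, SD and maximum like an observed duration. Read literally, it also replaces a later true end date held on the CRF.

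The cut-off differs by dose. It falls about 3 to 5 weeks after Dose 1, about 5 to 12 months after Dose 2, and nowhere after Dose 3. Two reactions with the same course can therefore receive different durations only because they followed different doses. A reader looking for persistent reactions will look at the maximum, and that value may come from the visit schedule. At stake is the descriptive duration table within the safety report.

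**Working it through.** The documents give no figure for reaction duration, so there is nothing to reproduce. The check applies the SAP rule to the protocol's dosing intervals.

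**Inputs.** Dose 2 is given 21-35 days after Dose 1, and Dose 3 is given 150-365 days after Dose 2 (Protocol 6.1). The diary covers Days 1-7, so onset lies 0 to 6 days after vaccination. Duration = end date - start date + 1 (SAP 3.5.2.1).

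**Value assigned to a reaction ongoing at the next dose** = interval - onset offset + 1.

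- Dose 1: shortest 21 - 6 + 1 = 16 days; longest 35 - 0 + 1 = 36 days. With Day 1 onset: 22-36 days.
- Dose 2: shortest 150 - 6 + 1 = 145 days; longest 365 - 0 + 1 = 366 days. With Day 1 onset: 151-366 days.
- Dose 3: no later vaccination, so no assigned value. A CRF end date is used in full if obtained; otherwise the duration is unknown.

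**Effect on the summary (assumed example).** Suppose 20 participants report a reaction, 19 of them for 2 days (total 38), and one for T days with Day 1 onset. The next dose comes at 28 days (cut at 29) after Dose 1 and at 180 days (cut at 181) after Dose 2.

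| T | Dose | Mean | Maximum | Unknown |
|---|---|---|---|---|
| 20 | Dose 1, Dose 2, or Dose 3 with known end | (38+20)/20 = 2.90 | 20 | 0 |
| 60 | Dose 1 | (38+29)/20 = 3.35 | 29 | 0 |
| 60 | Dose 2 | (38+60)/20 = 4.90 | 60 | 0 |
| 60 | Dose 3, end known | (38+60)/20 = 4.90 | 60 | 0 |
| 60 | Dose 3, end never obtained | 38/19 = 2.00 | 2 | 1 |
| 200 | Dose 1 | (38+29)/20 = 3.35 | 29 | 0 |
| 200 | Dose 2 | (38+181)/20 = 10.95 | 181 | 0 |
| 200 | Dose 3, end known | (38+200)/20 = 11.90 | 200 | 0 |
| 200 | Dose 3, end never obtained | 38/19 = 2.00 | 2 | 1 |

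The median is 2 days in every row. A reaction that ends before the next dose, with a known end date, is treated alike at all doses. The 60-day case shows that Dose 1 and Dose 2 already differ when the true end date is known. The maximum of 29 for Dose 1 carries no sign that the reaction was still present.

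**The case against.** The strongest case for the plan has three parts. First, stopping a dose-specific duration at the next dose has a rationale: symptoms after that point may belong to the new vaccination. Second, the table is descriptive, the SAP plans no comparison of durations between doses, and it already reports the median. Third, few reactions are likely to last long enough to matter: at least 16 days after Dose 1, or 145 days after Dose 2. All of this stands. It supports keeping a cut-off, but not presenting the cut value as a completed duration.

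Four stronger readings are tempting, and the documents do not support them:

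- *A persistent reaction after Dose 3 is always set to missing.* Stop dates are collected at Visit 5 (Protocol 8.11.5), investigator follow-up of AEs runs past the collection period until resolution or stabilisation (Protocol 8.3.1), and a known CRF end date is used. The missing rule covers every dose and operates only when no end date is known.
- *Reactions with no end date are dropped.* They leave the mean, median and range but are counted as unknown, and the participants stay in the incidence and severity tables.
- *The SAP ends a systemic event at the last diary entry when the diary stops before Day 7.* SAP 3.5.2.2 does say that "for all ongoing systemic events on Day 7, the stop date will be recorded in the CRF", but that sentence concerns recording and excludes no other stop date. Duration follows SAP 3.5.2.1, and the protocol visits already instruct sites to "collect stop dates of any e-diary events ongoing on the last day that the e-diary was completed and record stop dates in the CRF".
- *The distortion is large.* That needs a reaction that never resolves combined with a long Dose 2 to Dose 3 interval, and the documents give no rate for such events.

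**Conclusion.** The point holds as a minor reporting defect. A reaction known to be ongoing at the next vaccination is entered as if it ended that day, at 16-36 days after Dose 1 and 145-366 days after Dose 2, and nothing in the table shows it. The mean, SD and maximum for such reactions are not comparable across the three doses. In the assumed example, one 60-day reaction among 20 reporters gives a mean of 3.35 and a maximum of 29 after Dose 1, against 4.90 and 60 after Dose 2.

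The ranges follow from the SAP formula, the protocol windows and onset on Days 1-7. The example means rest on assumed durations and show direction only; the real size depends on the unknown number of such reactions. The primary safety estimands are percentages of participants reporting events (Protocol 9.1.1.2), so they do not change. Severity results and the immunogenicity test do not change either.

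**What to change.** In SAP 3.5.2.1 and 3.5.2.2, state that a reaction ongoing at the next vaccination, or ongoing at last contact after Dose 3, has no observed end. In SAP 6.1.2.2, for each dose:

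- report the number of such durations beside the number of unknown durations;
- leave them out of the mean, SD and maximum of completed durations, and show an affected maximum as 'at least x days';
- list each one with its minimum known duration and any later CRF end date.

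In the 60-day example, Dose 1 would then show 19 completed durations with a mean of 38/19 = 2.00, one reaction ongoing at the next vaccination, and a maximum of at least 29 days. The listing would give 29 days as the minimum and 60 days from the CRF. Dose 2 would still show a mean of 4.90, so the means need not agree, but the reason would be visible.

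The cost is a few SAP sentences, one more column and one listing, with no new data. The downside is that the mean then covers completed durations only. Kaplan-Meier medians are optional; for events this rare the count and listing are enough.
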